Pancreatic Enzyme Replacement
Therapy for treatment of Exocrine
Pancreatic Insufficiency in Patients with
Unresectable Pancreatic Cancer

NCT02985801

May 15, 2018

IRB Minimal Risk Protocol Template

Note: If this study establishes a human specimen repository (biobank) for research purposes, do not use this template. Use the Mayo Clinic Human Specimen Repository Protocol Template found on the IRB home page under Forms and Procedures at <http://intranet.mayo.edu/charlie/irb/>

First-time Use: Use this template to describe your study for a new IRB submission.

1. Complete the questions that apply to your study.
2. Save an electronic copy of this protocol for future revisions.
3. When completing your IRBe application, you will be asked to upload this template to the protocol section.

Modification: To modify this template after your study has been approved:

1. Open your study in IRBe. Click on the study 'Documents' tab and select the most recent version of the protocol. Save it to your files.
2. Open the saved document and activate "Track Changes".
3. Revise the protocol template to reflect the modification points, save the template to your files
4. Create an IRBe Modification for the study and upload the revised protocol template.

General Study Information

Principal Investigator: [name].

Study Title: Pancreatic Enzyme Replacement Therapy for treatment of Exocrine Pancreatic Insufficiency in Patients with Unresectable Pancreatic Cancer

Protocol version number and date: version 5, 5/15/2018

Purpose

Hypothesis:

Pancreas enzyme replacement therapy (PERT) decreases weight loss and improves quality of life in patients with unresectable pancreatic cancer.

Aims, purpose, or objectives:

1. Assess prevalence of pancreatic exocrine insufficiency (PEI) with fecal elastase-1 test (FE1) in patients with unresectable pancreatic cancer, without evidence of pancreatic duct (PD) or common bile duct (CBD) obstruction based on MRI or / and EUS.
2. Patients with PEI (FE1 <200) receive Pertzye or placebo in a cross-over fashion, each for 4 weeks. 3 capsules are taken with or after meals and 2 capsules with or after snacks (approximating 500 lipase units/kg/meal).

3. Body weight, body mass index (BMI), body composition (Bodystat Bioimpedance), are measured at the time of diagnosis of PEI and at 4 and 8 weeks of cross-over treatment. Baseline measurement of Vitamin D-25, Vitamin A, iron (ferritin, TIBC, iron), Vitamin B12, Tissue transglutaminase IgA (tTG) with total Immunoglobulin A (IgA)
4. Quality of Life (pain, diarrhea, weight, bloating, etc.) assessed at 0,4,8 weeks with
 - a.
 - b. Functional Assessment (FACT-Hep) for physical, social, emotional, and functional QOL²

Background

Pancreatic exocrine insufficiency (PEI) is a known complication of pancreatic cancer. Several mechanisms of PEI have been described in context of pancreatic cancer, including pancreatic atrophy secondary to tumor induced pancreatic duct obstruction and pancreatic fibrosis, both leading to PEI in patients with unresectable pancreatic cancer.³

Although the majority of patients with pancreatic cancer are inoperable at the time of diagnosis, only few authors addressed PEI in this patient cohort. Small studies with 8 to 12 patients detected PEI in 75% to 100%. The prevalence of PEI tended to be higher in setting of significant pancreatic duct obstruction.^{4,5} The largest cohort study included 194 patients with advanced pancreatic cancer which was defined as metastatic or unresectable due to local invasion. 50% of study participants had PEI.⁶ As a next step, Sikkens et al prospectively assessed the progression of PEI in 32 patients with unresectable cancer of the pancreatic head region. Based on FEI testing, 67% of patients had PEI at the time of pancreatic cancer diagnosis and 89% at 2 months follow up (median).⁷

Despite a high prevalence of PEI in patients with unresectable pancreatic cancer, clinical symptoms like steatorrhea are not uniformly present. In fact, 2 hallmark studies, including one with 12 and one with 194 patients, found no statistically significant correlation between the dyspepsia, number of bowel movements on the one hand and the presence of fat malabsorption on the other hand in patients with unresectable pancreatic cancer. Only 16.7% of patients with very severe PEI had clinically evident steatorrhea, whereas 5.2% of patients had subjective steatorrhea without PEI.^{5,6} Weight loss is another well-known complication of pancreatic cancer. Perez et al. who found a significant correlation between fat-protein malabsorption and weight loss in non-surgical patients with pancreatic cancer however not between diminished caloric consumption and weight loss.⁵

As of now, multiple studies showed improved fat absorption with pH-sensitive microsphere formulation in comparison to conventional pancreatic enzyme preparations or placebo in chronic pancreatitis patients with PEI.⁸⁻¹⁴ However, only few studies addressed the utility of PERT for patients with inoperable pancreatic cancer, including a randomized study by Bruno et al. with 21 patients with unresectable pancreatic cancer and pancreatic duct obstruction. Patients randomized into PERT for 4 weeks had reduced weight loss compared with patients who were treated with placebo.¹⁵ A retrospective study by Domínguez-Muñoz et al. included 76 patients with inoperable pancreatic cancer. Patients who received PERT (Creon[®]) had a longer median survival than patients with palliative therapy alone.¹⁶ Of note, PEI was not formally assessed in either of those studies. Based on these limited results current pancreatic cancer guidelines recommend PERT for patients with unresectable pancreatic cancer, in the realm of palliative therapy.¹⁷ However the efficacy of PERT in patients with unresectable pancreatic cancer was never proven in a randomized controlled trial.

A further concern is the adverse drug reaction profile of PERT. In adult population no severe side effects of PERT are documented. Hyperuricosuria and especially colonic fibrosis are the most feared severe adverse drug reaction (ADR) of long term PERT, however they were reported only in children with cystic fibrosis.^{18,19, 20,21}

However dyspepsia, heartburn and bloating are well described mild ADR of PERT. In this context, several randomized controlled trials revealed a higher incidence of bloating and abdominal pain in patients who received PERT for PEI for mostly benign pancreatic conditions.^{21,22,23,24} The impact of ADR on the quality of life was never assessed in a randomized controlled fashion in patients with unresectable pancreatic cancer. Finally, the high costs of PERT, which range up to \$2000 a month, emphasize the importance to clarify the pros and cons of PERT for patients with unresectable pancreatic cancer, to avoid unnecessary and costly treatments.

Subject Information – charts, records, images, or specimens are considered ‘subjects’

*Target accrual is the proposed number of subjects to be included in your study at your site. “Subjects” may include Mayo Clinic charts, records, or specimens, **and/or** charts, records, or specimens received at Mayo Clinic from external sources for collaborating analysis by the investigator under this IRB application:*

Target accrual:
30 completed patients

Subject population:

Inclusion Criteria:

- Patients 18- 100years
- Underlying pancreatic adenocarcinoma, unresectable (local invasion or distant metastasis)
- On established chemotherapy regimen for pancreas cancer, which will be continued over the time of study
- Fecal elastase-1 test (FE1) less than 200 mcg pancreatic elastase/g stool

Exclusion Criteria:

- Common bile duct obstruction resulting in obstructive jaundice
- Celiac disease
- Crohn’s disease
- Benign pancreatic conditions
- Bowel obstruction
- Surgically altered bowel anatomy

Yes No Will a Certificate of Confidentiality (COC) be obtained from NIH? If yes, Who is obtaining the COC: Mayo Clinic investigator, study sponsor, other:
Explain why a COC is needed:

Study Design

Methods:

Patients with unresectable pancreatic adenocarcinoma (local invasion or distant metastasis) receive pancreatic enzyme replacement therapy (PERT) by the oncology team as presumed standard of care. Patients will be offered to participate in study, which lasts 10 weeks.

Pancreatic enzyme insufficiency (PEI) will be detected by (fecal elastase-1) FE1 testing. Patients with FE1 less than 200 mcg pancreatic elastase/g stool are eligible for study. Patients will be randomized into first placebo or first treatment group (cross over study) by enclosed envelope.

Patients will received either Pertzye (Pancrelipase) 500 lipase units/kg/meal or placebo, each for 4 weeks. Dosing will be 3 capsules 3 times a day with or after meals and 2 capsules with or after snacks. No treatment will be administered at weeks 5 and 6 to assure adequate washout. Pertzye or placebo will be given for another 4 weeks (week 7 - 10) in a cross-over fashion.

Body weight, body mass index (BMI), body composition (Tanita, TBF-310GS, Bodystat Bioimpedance), FACT-Hep quality of life assessment will be measured at randomization and at last day of treatment or placebo (week 4 and 10).

Resources:

Patients will be recruited in oncology or gastroenterology clinic by oncology fellow or gastroenterology fellow in the setting of their regular clinical work.

Pertzye and placebo will be sponsored by pharmaceutical company.

Check all that apply. If none apply, leave blank:

- This is a multisite study involving Mayo Clinic and non-Mayo Clinic sites.
When checked, describe the research procedures/activities being conducted **only** at Mayo Clinic:
- Mayo Clinic staff will be engaged in research activity at a non-Mayo Clinic site. *When checked, provide the location and a detailed description of the Mayo Clinic research staff involvement.*
- This study is to establish and/or maintain an ongoing database or registry for research purposes only.
- The research involves contact or interaction with subjects, for example, surveys, questionnaires, observation, blood draw.
- The study involves photographing, audiotaping or videotaping subjects (and guests).

Review of Chart, Images, Specimens

Provide the date range for collection of data and/or specimens that will be included in your research dataset.

Check all that apply:

- This study involves only data and/or specimens that exist at the time this application is submitted to the IRB (IRB submission date). No data or specimens will be collected beyond this date.

This study involves only data and/or specimens that will be collected after submission to the IRB.

The study involves data and/or specimens that exist at the time of submission to the IRB **and** data and/or specimens that will be collected after submission to the IRB, for example a study that includes collection of existing data and prospective collection of specimens.

Data and/or specimens used in this study are collected under another IRB protocol. *When checked, provide the IRB number(s) from which the research material will be obtained. When appropriate, check the box below to attest that subjects have provided consent for future use of their data and/or specimens, as described in this protocol.*

IRB Number/s - Data Only: _____

IRB Number/s - Specimens Only: _____

IRB Number/s - Data and Specimens: _____

Note: When subjects provided consent for use of their data and/or specimens, as described in this protocol.

Other data sources will be utilized in this study, e.g. receiving data/specimens from an external party. When checked, provide all data sources:

Data Confidentiality, HIPAA Subject Identifiers

Review the list of subject identifiers below and, if applicable, check the box next to each subject identifier being recorded at the time you are collecting/abstracting data/specimens for use in this study.

Subject Identifiers: Individually identifiable information, including demographic data, that identifies the individual or for which there is reasonable basis to believe it can be used to identify the individual. **NOTE:** Identifiers apply to subjects enrolled in your study and to the subject’s relatives, household members, employers, etc.

Internal refers to subject identifiers that will be included in the dataset maintained by the study team.

External refers to subject identifiers that will be shared with persons outside of the immediate study team, for example, sent to an external collaborator or shared with a national registry.

SUBJECT IDENTIFIERS Check all that apply	INTERNAL IDENTIFIER	EXTERNAL IDENTIFIER
Name	x	
Social Security number		
Medical record/patient registration number, lab accession, specimen or radiologic image number	x	

Study number, subject ID, or any other unique identifying number, characteristic or code that can be used to link the identity of the subject to the data	x	
Dates: All elements of dates [month, day, and year] directly related to an individual. Their birth date, date of death, date of diagnosis, etc. Note: Recording a year only is not a unique identifier.	x	
Medical device identifiers and serial numbers		
Biometric identifiers, including finger and voice prints, full face photographic images and any comparable images		
Web Universal Resource Locators (URLs), Internet Protocol (IP) address numbers, email address		
Street address, city, county, precinct, zip code, and their equivalent geocodes		
Phone or fax numbers		
Account, member, certificate or professional license numbers, health beneficiary numbers		
Vehicle identifiers and serial numbers, including license plate numbers		
If None of the above identifiers will be recorded or maintained in the dataset and/or sent outside of the study team, please check "None".	 None	 None

Statistical Information

Statistical Considerations

Data Analysis Plan and Power Statement:

Statistical significance will be calculated with pair t-test.

According to Bruno et al and Dominguez-Munoz et al a 5% weight difference between the treatment groups is expected within 4 weeks. Standard deviation is expected to be less than 5% based on the cross over fashion. Assuming a patient drop out of 30%, a minimum of 13 patients need to be included in the trial to detect a statistically significant difference, with a power of 80% and alpha error of 5%. Eventually, we target to include 30 patients to assure adequate power, given the statistical limitations of previously reviewed studies.

Endpoints

Primary:

1. Weight change

Secondary:

1. Quality of life (QOL)
2. Change in body composition

References

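### The only planned test, a paired t-test, has no period term although the second-period weight change appears to include the two untreated washout weeks; adding one is a cheap, minor improvement

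*Combined protocol and SAP*

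**What the plan says.** The Data Analysis Plan and Power Statement gives the whole analysis in one sentence: "Statistical significance will be calculated with pair t-test". No section adds a period, sequence or carryover term. The primary endpoint is listed only as weight change, and no starting weight is defined for the second period.

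The design is a two-sequence crossover: "Patients will be randomized into first placebo or first treatment group (cross over study) by enclosed envelope". Neither the allocation ratio nor any blocking is stated. On the gap between periods, the Methods say: "No treatment will be administered at weeks 5 and 6 to assure adequate washout". The second treatment period is weeks 7 to 10. Weight and the other measures "will be measured at randomization and at last day of treatment or placebo (week 4 and 10".

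The Aims give different times: the measures "are measured at the time of diagnosis of PEI and at 4 and 8 weeks of cross-over treatment". Neither section lists a weight at the start of the second period.

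The power statement plans on a 5% weight difference over four weeks, 30% dropout, 80% power and a 5% alpha error. On variability it says "Standard deviation is expected to be less than 5% based on the cross over fashion". It gives a minimum of 13 patients and a target of 30 to be included; the Subject Information section sets the target at 30 completed.

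**The concern.** On the Methods' times, the first-period change runs from randomisation to week 4 and the second, if measured from the week-4 weight, from week 4 to week 10. The second therefore contains two extra weeks without treatment. The Background gives a reason to expect movement in those weeks: "Weight loss is another well-known complication of pancreatic cancer". The hypothesis also presupposes ongoing loss: "Pancreas enzyme replacement therapy (PERT) decreases weight loss and improves quality of life in patients with unresectable pancreatic cancer".

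Whatever patients lose on average during the washout is charged to the treatment that comes second. A paired t-test pools the two sequences without separating this out. If the sequences finish with unequal numbers, part of the washout loss enters the treatment estimate and its confidence interval. If they finish with equal numbers, it enters the error variance instead.

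**Working it through.** **Plan's own figure.** Paired t-test, difference 5, SD of the within-patient difference 5, two-sided 5%: 10 completers give power 80.3%, and 10 × 1.3 = 13, the stated minimum. The power statement therefore fits a plain paired t-test. (Dividing by 0.7 instead would give 15; this does not matter at a target of 30.)

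**Inputs.**
- From the documents: difference 5%, SD at most 5%, dropout 30%, target 30.
- Completers: 30 × 0.7 = 21 if 30 are included; 30 if 30 are completed.
- Assumed: w, the average percent lost in the washout, from 0 to 2.5. The upper value is half of a 5% four-week untreated loss, itself an assumption.
- Assumed: SD 5.59 for the paired difference. Splitting 25 equally gives variance 12.5 for a four-week change; scaling with time gives 12.5 × 6/4 = 18.75 for six weeks; √(12.5 + 18.75) = 5.59.

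**Model.** D is Pertzye change minus placebo change; AB is Pertzye first, BA placebo first; δ is the true effect.
- Mean of D: δ + w in AB, δ − w in BA.
- The paired estimate averages all n values, so its mean is δ + w(nAB − nBA)/n.
- Between-sequence variance left in the test: 4w²·nAB·nBA/n², which is w² at equal numbers. At w = 2.5 and 15:15 the variance rises from 31.25 to 37.5.
- The period-adjusted estimate is half the sum of the two sequence means: [(δ + w) + (δ − w)]/2 = δ for any split. Its standard error is (s/2)√(1/nAB + 1/nBA), where s is the pooled within-sequence SD, on n − 2 degrees of freedom.

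**Error with no treatment effect** (simulation, w = 2.5, SD 5.59, nominal two-sided 5%):

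| Completers AB:BA | Shift (points) | Paired, two-sided | Period-adjusted |
|---|---|---|---|
| 12:9 | 2.5 × 3/21 = 0.36 | 4.0% | 5.0% |
| 13:8 | 2.5 × 5/21 = 0.60 | 5.3% | 5.0% |
| 14:7 | 2.5 × 7/21 = 0.83 | 7.4% | 5.0% |
| 16:14 | 2.5 × 2/30 = 0.17 | 3.4% | 5.0% |
| 17:13 | 2.5 × 4/30 = 0.33 | 4.1% | 5.0% |
| 18:12 | 2.5 × 6/30 = 0.50 | 5.2% | 5.0% |
| 20:10 | 2.5 × 10/30 = 0.83 | about 9% | 5.0% |

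The mirror splits give the same error with the shift reversed. At w = 1.5, 14:7 gives about 6%. A 12:9 split would arise from 15:15 if, for example, 20% of Pertzye-first and 40% of placebo-first patients dropped out (15 × 0.8 = 12; 15 × 0.6 = 9). Under simple 1:1 allocation, 14:7 or worse in one named direction has probability 0.095 and 20:10 or worse 0.049; blocking would lower both. Averaged over simple allocation of 21, the paired test's error is 5.0%.

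**Power, paired against period-adjusted** (SD 5.59, w = 2.5 unless stated):
- True 5%: 0.97 against 0.97 at 11:10; 0.995 against 0.997 at 15:15.
- True 3% (assumed): 0.61 against 0.65 at 11:10; 0.75 against 0.81 at 15:15.
- Minimum size only, 13 × 0.7 = 9.1 completers, true 5%, SD 5: 0.71 against 0.73 at 5:4; 0.60 against 0.72 at 4:5.

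**Aims timing.** If the Aims' week 8 is a calendar week, both intervals are four weeks and a steady background drift shifts neither sequence, though the second interval would hold only two treated weeks (7 and 8). If it counts weeks of treatment, it is calendar week 10 and the results above apply.

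**The case against.** The strongest reply is that randomisation already protects the test. Over 1:1 allocation, with dropout unrelated to sequence, the paired test has 5.0% error at every w, and it is conservative when the split is near even. At the planned effect and target size almost no power is lost. All of that stands. What it leaves is conditional: the realised split is known at analysis, and the reported estimate and interval carry that split's shift.

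A reader might infer that the planned test has an inflated false-positive rate, or that it favours Pertzye. The documents do not support either. The error exceeds 5% noticeably only when a marked imbalance and an assumed w near 2.5 coincide, and the direction depends on which sequence has more completers.

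The missing figure for w also stands as an objection. When w is below about 1 to 1.5%, the period term costs slightly more power than it saves, so the documents cannot show a net power gain. The week-4 starting point for period 2 is likewise inferred from the weighing times.

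A reader might also infer that a period term removes the washout problem altogether. It does not. A washout loss that differs by preceding treatment, carryover, and the extra random variation of a six-week interval all remain. A weight at the end of week 6 would address the interval mismatch directly.

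**Conclusion.** The point holds as a minor one. It is well supported that the only named test lacks a period term and that the Methods' weighing times leave the washout inside the second interval if week 4 is its baseline.

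The size is less certain, because w is assumed. At w = 2.5 the shift is 7% of the planned 5% difference at 12:9 (0.36/5) and 17% at 14:7 or 20:10 (0.83/5); at w = 0 there is none. The 14:7 and 20:10 error rates are worst cases. Nothing here shows that the trial is underpowered at its target or that the test is invalid on average. The case for changing it is that the standard crossover analysis makes the estimate independent of the realised split at very small cost.

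**What to change.** Replace the paired t-test sentence with:

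> Primary analysis: period-adjusted two-sequence t-test (treatment and period as fixed effects, patient as fixed effect) on percent weight change per period (week 4 minus randomisation; week 10 minus week 4) in patients with both periods. The treatment difference is given with its 95% CI, and completers are reported by sequence.

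Reconcile the measurement times in the Aims with those in the Methods, and the target of 30 completed in Subject Information with the target of 30 included in the power statement. If the reconciled times are not week 4 and week 10, the change definitions must follow them.

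The cost is analysis wording and one degree of freedom; no patients or visits are added. With no drift and SD 5, power at a true 5% goes from 0.80 to 0.79 at 5:5 completers. With 21 completers, SD 5.59 and w = 0, averaged over simple allocation, it goes from 0.97 to 0.96 at a true 5% and from 0.65 to 0.62 at a true 3%.

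### The stated minimum of 13 included patients does not give 80% power at the plan's own SD bound of 5% with a two-sided paired t-test; 15 are needed, and the target of 30 is unaffected

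*Combined protocol and SAP*

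**What the plan says.** Everything needed is in the Statistical Information section, under Data Analysis Plan and Power Statement:

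- Test: "Statistical significance will be calculated with pair t-test".
- Effect: "a 5% weight difference between the treatment groups is expected within 4 weeks".
- Variability: "Standard deviation is expected to be less than 5% based on the cross over fashion". No other SD is given.
- Error rates: "with a power of 80% and alpha error of 5" percent. Sidedness is not stated.
- Dropout and sample size: "Assuming a patient drop out of 30%, a minimum of 13 patients need to be included in the trial".

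Dropout and the number to be included stand in the same sentence, so 13 is the count before losses. The plan does not give the number of completers behind it or the inflation formula. The paragraph then moves to a target of 30 included patients. The Target accrual entry under Subject Information also gives 30, but as patients who complete.

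**The concern.** Thirteen is the only sample size that the protocol ties to its 80% power claim. The target of 30 has no calculation of its own. If 13 does not follow from the inputs beside it, the one power calculation in the document cannot be relied on as written.

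The number also looks like a familiar slip. To keep n completers after losing a fraction d, one includes n/(1 − d). Multiplying by (1 + d) always gives too few, and the gap is noticeable when d is as large as 30%. At stake is the accuracy of the stated minimum, and what a reader would conclude about a trial of about that size.

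**Working it through.** **Inputs** (all from the power statement unless marked)

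- Mean within-patient difference: 5%.
- SD: 5%, the upper bound and the only figure given. Assumption: it is the SD of the paired difference. The standardised effect is then 5/5 = 1.0.
- Alpha 5%. Assumption: two-sided. One-sided is tried below.
- Power 80%, dropout 30%, stated minimum 13.

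**Step 1: completers needed.** Paired t-test power comes from the noncentral t distribution with n − 1 degrees of freedom and noncentrality 1.0 × √n.

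| Completers | Two-sided 5% | One-sided 5% |
|---|---|---|
| 7 | 60.0% | 75.4% |
| 8 | 68.1% | 81.5% |
| 9 | 74.8% | 86.2% |
| 10 | 80.3% | 89.8% |
| 11 | 84.8% | 92.4% |

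Two-sided, 10 completers is the smallest number that reaches 80%.

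**Step 2: reproducing 13.** 10 × 1.3 = 13.0, exactly the stated figure. At an SD of 5%, correct inflation by other routes does not give 13:

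- one-sided t-test: 8/0.70 = 11.4, so 12;
- two-sided normal approximation: 8 completers, so again 12;
- one-sided normal approximation: 7/0.70 = 10.

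**Step 3: correct inflation.** 10/(1 − 0.30) = 14.3, so 15 included.

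**Step 4: what 13 delivers.** 13 × 0.70 = 9.1, so about 9 completers and 74.8% power (two-sided). If the number of completers is treated as binomial with probability 0.70, average power is 73.8% with 13 included, 77.7% with 14 and 81.1% with 15. With 13 included, the chance of fewer than 10 completers is 58%.

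**Step 5: sensitivity to the SD.** Two-sided, 9 completers reach 80% only if the SD is 4.69% or less:

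| SD | Power with 9 completers |
|---|---|
| 4.5% | 83.0% |
| 4.6% | 81.4% |
| 4.7% | 79.8% |
| 4.8% | 78.1% |
| 4.9% | 76.5% |
| 5.0% | 74.8% |

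With an SD between about 4.33% and 4.69%, exactly 9 completers are needed, and 9/0.70 = 12.9 gives 13 by correct inflation.

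**Step 6: the target of 30.** If 30 are included, 30 × 0.70 = 21 complete and power is 99.2%. If 30 complete, power is over 99.9%, and 30/0.70 = 42.9, so about 43 would have to be included.

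**The case against.** Three objections carry weight.

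**The multiplication by 1.3 is inferred.** A reader might take the exact match as proof of the slip. The documents do not support that: they show neither a formula nor a completer count. The SD is described as below 5%, and a value of 4.5% or 4.6% gives 13 with correct inflation. So the mechanism stays a likely explanation only. What remains is that 13 fails at the one SD figure given, and a minimum justified by an upper bound should hold at that bound.

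**Sidedness is open.** The hypothesis is directional, although that alone does not make the test one-sided. At one-sided 5%, 9 completers give 86.2%, and 13 included give 85.0% averaged over binomial dropout, so 13 would be adequate. The shortfall is therefore conditional on a two-sided test.

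**Nothing depends on 13.** A reader might infer that 13 is an accrual floor on which the sponsor would fall back, or that the trial is underpowered. The documents support neither. They attach no stopping point or decision rule to 13, and the power statement itself goes on to 30. On the plan's own inputs that target has ample power. This limits the consequence to the written justification, but it does not make the stated minimum right.

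**Conclusion.** The point holds as a minor correction. At an SD of 5% and two-sided 5%, the minimum consistent with 80% power and 30% dropout is 15 included, two more than stated. At 13 the power is 74.8%, about 5 points below the claim.

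This rests on reading the 5% as the SD of the within-patient difference, on taking it at its bound, and on a two-sided test. Dropping either of the last two can rescue 13: an SD of about 4.69% or less, or a one-sided alpha. The plan commits to neither. The finding concerns one number in the power statement and is not evidence that the trial is underpowered on its own assumptions.

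**What to change.** In the power statement:

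1. Replace the minimum of 13 with 10 completers and 15 included, at SD 5% and two-sided 5%. Alternatively keep 13, and state the smaller SD or the one-sided alpha that supports it.
2. State the sidedness and the number of completers before inflation.
3. Decide whether the target of 30 means included (power statement) or completed (Target accrual), and make the two sections agree. Then quote power at the target: 99.2% with 21 completers, or over 99.9% with 30.

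The cost is a corrected number and a sentence or two. The first two changes add no patients. The third only settles a count on which the two sections already differ; if completed patients are meant, about 43 inclusions follow from the plan's own dropout rate.
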